1. BACKGROUND, EARLY CHILDHOOD CARIES

Early Childhood Caries (ECC) is a pandemic in the US, particularly within poor minority populations where ECC rates are as high as 90%.¹ The etiology of this disease is thought to include bedtime bottle feeding and vertical transmission of cariogenic bacteria (i.e. Strep. Mutans) from mother to child. Mandibular incisors are generally protected from the cariogenic bacteria and carbohydrates because of the resting position of the tongue over the lingual surfaces of those teeth, leaving maxillary incisors exposed to both bacteria and carbohydrates.² Treatment for ECC is expensive, ranging from \$1,000 or more. In addition, ECC's have a large impact on the child's health like low weight gain.³

Historically, stainless steel crowns (SSC) have been the most reliable and predictable in longevity. However for the anterior teeth, it is unattractive because of the display of metal. Demand for more esthetic restorations has been on the rise. A procedure was presented exploring an open faced crown technique, where the operator cements a traditional SSC, opens a window on the facial aspect of the crown to fill and shape the tooth colored resin material. This procedure demands more chair time and is also technique sensitive.⁴ By the 1990's, pre-veneered stainless steel crowns (PVSSC) had been on the market with names such as NuSmile crowns, Kinder Krowns and Cheng Crowns. NuSmile crowns have shown success by having the strongest veneer facing against shear forces, parental acceptance of esthetics, and are less technique sensitive.⁵⁻⁷

PVSSC are SSC bonded with thermoplastic composites on the roughened or meshwork facial surfaces. It is made from the same SSC used by dentists for many years. Many advantages of these crowns are noted. Parents find the PVSSC's to be esthetically acceptable, hemorrhaging does not affect the resistance or retention, or color of the crown, and there is less chair time needed when compared with alternative restorations.⁶ Nevertheless, no system is without disadvantages. The operator is limited to crimping only on the lingual surface of the crown because crimping the facial may cause the veneer to chip off. This leads to limited adaptability of the crown to the tooth surface. In addition, there are only two shades available, making exact colors matching very difficult for a single tooth. Overall, the PVSSCs cost more money than SCCs or direct resin restorations.⁸ Recently, NuSmile introduced a new type of anterior crowns, the NuSmile ZR. It is made of high grade monolithic zirconia ceramic which provides strength, durability and esthetics characteristics to these crowns.

With the variety of options for restoring anterior primary teeth, it is of interest to evaluate the long term success of PVSSC, zirconia and composite in terms of durability, esthetics and cost effectiveness for the treatment of anterior primary teeth.

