2. PURPOSE

Notably literature has focused on individual operator experience with the product and comparing bonding strengths of the PVSSC's composite surface, as well as autoclavability of PVSSCs⁸, clinical success with NuSmile crowns⁹, and their failure strengths.¹⁰ However, most of the literature mentioned early in dealing with resistance, retention and shear forces of the PVCCs are done on bench top or operator experience

describing clinical cases. Very few randomized control trials were done on the clinical success of PVSCCs and zirconia ceramic crowns.

The purpose of this pilot study is to evaluate the clinical performance of PVSCC and zirconia crowns compared to composite crowns as definitive treatment for multi-surfaced affected anterior primary teeth.

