3. OBJECTIVES

The objective of this pilot study is to assess the clinical performance of NuSmile's Pre-Veneered Stainless Steel Crown – NuSmile Signature and NuSmile ZR compared with composite crowns - Success Essentials esthetic temps/strip crowns - at the Center for Pediatric Dentistry, Seattle, Washington.

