6. STUDY POPULATION

Ninety (90) subjects contributing to approximately 120 to 200 crowns on primary teeth will be recruited from the patient pool of the Center for Pediatric Dentistry who receive care under general anesthesia and enrolled into the study. A maximum of four crowns will be placed in any subject. It is estimated that it will take approximately 24 weeks to place all crowns and complete the baseline examination.

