10. STUDY ASSESSMENTS

Clinical Assessments will be done at baseline post crown placement; at months 3, 6, 12 and 18; and end of study visit occurring in range of 24 to 30 months from baseline.

Assessments and documentation required at each assessment interval:

• Photographs of selected teeth	Baseline
• Photographs of tooth preparations	Baseline and when possible
• Photographs of cemented crowns	Baseline
• Photographs of occlusal and frontal views	Baseline and when possible
• Assessment of fit	All intervals
• Assessment of positioning	All intervals
• Assessment of proximal contact	All intervals
• Assessment of marginal adaptation	All intervals
• Assessment of color: match , staining/color change	All intervals
• Assessment of time placement	Baseline
• Assessment of gingival status	All intervals
• Assessment of retention	3, 6, 12, 18 and 24 mo
• Assessment of veneer/composite integrity	3, 6, 12, 18 and 24 mo
• Assessment of secondary caries	3, 6, 12, 18 and 24 mo
• Assessment of trauma	3, 6, 12, 18 and 24 mo
• Assessment of clinical pulp pathology	3, 6, 12, 18 and 24 mo
• Assessment of radiographic pulp pathology	24 mo
• Assessment of tooth	All intervals
• Assessment of parents' esthetic satisfaction	All intervals (baseline at 3-month follow up)

Non-recall assessment to be done at the time of tooth/crown lost to study due to trauma. If this was to occur, the patient would be discontinued from study and the justification recorded.

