11.0 DATA ANALYSIS

Descriptive statistics (means, standard deviations, counts, and percentages) will be calculated for all variables. To evaluate if the primary efficacy variables differ by the three treatment groups (NuSmile PVSCC Signature Crowns, NuSmile ZR, and Strip composite crowns), ANOVA or Chi-square tests of association will be performed.

All subjects evaluated at the 6-month interval or beyond and subjects who have lost crowns or teeth will be considered for efficacy. All enrolled subjects defined here as those who have had at least one crown placed will be evaluated for safety. Any missing, unused or false data will be omitted from data analysis.

The primary efficacy variables in this trial are fit, positioning, proximal contact, marginal adaptation, color match, gingival status, crown retention, veneer/composite integrity, secondary caries, occlusal integrity, history of trauma, clinical pulp pathology, parents' esthetic satisfaction. Scores for efficacy variables will be summarized and displayed using descriptive statistics (means, standard deviations, counts, and percentages).

Inferential statistics will be used to detect significant differences in the primary efficacy variables by the treatment status at baseline and at 6, 12, 18, and 24 month follow-up. Statistical differences will be calculated using logistic regression models accounting for within cluster variance using generalized estimating equations (GEE).

Safety variables include Adverse Events and Unanticipated Adverse Device Effects. All subjects that have had crowns placed will be evaluated for safety. Descriptions of occurrences, incidence, severity and required treatments for Adverse Events and Unanticipated Adverse Device Effects Will be summarized and tabulated where appropriate.

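### Placement time is kept only as a three-band grade, with no statement of whether it is per crown or per child, so the trial can describe chair time only crudely

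*Combined protocol and SAP*

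**What the plan says.** Section 1 (Background) ends by saying it is of interest to "evaluate the long term success of PVSSC, zirconia and composite in terms of durability, esthetics and cost effectiveness". The same section lists shorter chair time among the advantages of pre-veneered crowns and higher price among their drawbacks.

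The formal aims are narrower. Section 2: "The purpose of this pilot study is to evaluate the clinical performance of PVSCC and zirconia crowns compared to composite crowns". Section 3: "The objective of this pilot study is to assess the clinical performance". Neither mentions cost or time.

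Section 10 lists "Assessment of time placement" at baseline only. Appendix 6 grades it A (30 minutes or less), B (over 30 and up to 45) or C (over 45). Section 8 does not list it.

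On crowns per child, Section 6.1 requires at least one and Section 6 sets the limit: "A maximum of four crowns will be placed in any subject".

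Section 11 promises descriptive statistics for all variables, without saying that they will be split by arm. Formal testing is narrower: "Inferential statistics will be used to detect significant differences in the primary efficacy variables by the treatment status". That list begins "The primary efficacy variables in this trial are fit, positioning, proximal contact, marginal adaptation, color match, gingival status, crown retention", goes on through "occlusal integrity, history of trauma, clinical pulp pathology" and ends with parental satisfaction. Placement time is not in it.

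**The concern.** Chair time is the one resource quantity that the trial sets out to measure, and the Background makes a claim about it. Two features of the measure weaken it.

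- **The unit of observation is undefined.** Two clinicians could grade the same case differently while both follow the protocol. Nor is it stated when timing starts and stops.
- **The grade is coarse.** If crowns usually take less than 30 minutes each and are timed singly, nearly all fall in band A whichever crown is used.

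The result would be a baseline table from which neither minutes per crown nor a difference between arms can be recovered. Placement happens once, so exact times that were not recorded cannot be obtained later. For a pilot, an estimate of placement time with an interval is useful planning information.

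**Working it through.** The plan states no figure for placement time, so there is nothing to reproduce. All minutes and SDs below are assumptions. The cut-points (30 and 45 minutes), the crown limits (1 to 4), the arm size (30) and the expected 120 to 200 crowns in 90 children come from Appendix 6 and Sections 5, 6 and 6.1.

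**1. Does the unit change the grade?** Time per child = minutes per crown × number of crowns, graded by Appendix 6.

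| Assumed min per crown | Grade per crown | Per child: 1 crown | 2 crowns | 3 crowns | 4 crowns |
|---|---|---|---|---|---|
| 8 | A | 8, A | 16, A | 24, A | 32, B |
| 10 | A | 10, A | 20, A | 30, A | 40, B |
| 15 | A | 15, A | 30, A | 45, B | 60, C |
| 20 | A | 20, A | 40, B | 60, C | 80, C |

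Per crown, every row is A. Per child, the grade can move by one or two bands.

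**2. How often would this matter?** Mean crowns per child are expected to be 120/90 = 1.3 to 200/90 = 2.2. At 8 to 15 minutes per crown, a child with one or two crowns is A either way. The ambiguity then affects children with three or four crowns. At 20 minutes it already affects those with two.

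**3. Can minutes be recovered from the grades?** No. An arm graded all A has a mean somewhere between 0 and 30 minutes. An assumed split of 50% A, 30% B and 20% C gives a mean of at least 0.3 × 30 + 0.2 × 45 = 18 minutes, with no upper limit because band C is open.

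**4. What does banding cost in precision?** Assume normal times, SD 8, one value per child, 30 per arm and two-sided 5% tests.

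Share in band A = Φ((30 − mean)/8):
- mean 15: Φ(1.875) = 0.970
- mean 20: Φ(1.25) = 0.894
- mean 25: Φ(0.625) = 0.734

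On minutes, the standard error of a difference is 8 × √(2/30) = 2.07. The standardised difference is 5/2.07 = 2.42, which on 58 degrees of freedom gives 66% power. The 95% interval has a half-width of about 2.00 × 2.07 = 4.1 minutes.

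| Analysis | 15 vs 20 min | 20 vs 25 min |
|---|---|---|
| t-test on minutes | 66% | 66% |
| Band A vs other, Fisher exact | 4% | 25% |
| Band A vs other, uncorrected chi-square | 19% | 37% |
| Rank test on all three bands | 19% | 37% |

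The band figures come from simulation. Direct enumeration of the Fisher and chi-square powers gives values within about one percentage point.

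**5. Is cost covered elsewhere?** No price, fee, material cost or retreatment cost is defined, and no cost-effectiveness measure. Section 11 tabulates treatments required for adverse events, but as a safety summary and not costed.

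**The case against.** The strongest reply is that this is a convenience-sample pilot of clinical performance. Placement time is a process measure with no power target, and counts by band are a natural pilot output. All the minutes above are assumed. Randomisation by child should balance crown count between arms on average, so the ambiguity adds noise and not systematic bias. With 1.3 to 2.2 crowns expected per child, many children would have the same grade under either reading.

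Most of this stands, and it limits the weight of the point. It does not remove it. The unit is undefined for a variable that the trial has chosen to collect, and banding loses power under every test tried. The lowest figure, 4%, depends on using Fisher's test. Section 11 names chi-square, for which the figure is 19%.

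A reader might infer more than the documents support:

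- **That the trial fails a cost-effectiveness objective.** The term appears only in the Background. Sections 2 and 3 name clinical performance alone.
- **That time has no unit, or will not be summarised at all.** The bands are in minutes, and descriptive statistics are promised for all variables. What is missing is the unit of observation, the timing rule and an inferential comparison.
- **That the per-child grade mainly reflects crown count.** This depends on placement times that the documents do not give.
- **That exact minutes are known and then discarded.** A band can be judged without exact timing, and the documents do not say what source records hold.

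**Conclusion.** The point holds as a low-cost improvement. Appendix 6 leaves the unit of observation open, so the same case can be graded differently: A per crown and C per child for four crowns at an assumed 15 minutes each. Banding reduces power for a 5-minute difference from about 66% to 4-19% or 25-37%, depending on the means and the test. These figures assume normal times, SD 8, one value per child and 30 per arm. The loss would be smaller if times lay closer to the cut-points. The chair-time claim can be examined only crudely and ambiguously as the plan stands.

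The plan cannot address cost effectiveness because no cost data are planned. That is a minor mismatch between the Background and the plan. It does not touch the trial's stated objective or its clinical endpoints.

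**What to change.** **Section 10 and Appendix 6.** Record placement start and stop time in minutes under a stated timing rule, for example from start of preparation to end of finishing, and the number of study crowns placed. Derive the three bands from these. The rule should say whether time spent on a crown that proves not to fit (Section 7.5.4) is counted.

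**Section 11.** Report minutes per crown by arm as a secondary, descriptive comparison, Signature vs strip and ZR vs strip, each with a 95% interval. Use one value per child (total minutes divided by study crowns), or account for clustering by child if crowns are timed separately.

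**Section 1.** Unless costs will be collected, limit the stated interest to placement time. This is editorial. Minutes alone do not give cost effectiveness, and no such conclusion should be drawn from them.

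**Cost.** Two extra baseline fields and one extra secondary comparison in a plan that already has 13 primary efficacy variables, which is why it should stay descriptive. The existing bands remain available.

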2. PURPOSE

Notably literature has focused on individual operator experience with the product and comparing bonding strengths of the PVSSC's composite surface, as well as autoclavability of PVSSCs⁸, clinical success with NuSmile crowns⁹, and their failure strengths.¹⁰ However, most of the literature mentioned early in dealing with resistance, retention and shear forces of the PVCCs are done on bench top or operator experience

describing clinical cases. Very few randomized control trials were done on the clinical success of PVSCCs and zirconia ceramic crowns.

The purpose of this pilot study is to evaluate the clinical performance of PVSCC and zirconia crowns compared to composite crowns as definitive treatment for multi-surfaced affected anterior primary teeth.

3. OBJECTIVES

The objective of this pilot study is to assess the clinical performance of NuSmile's Pre-Veneered Stainless Steel Crown – NuSmile Signature and NuSmile ZR compared with composite crowns - Success Essentials esthetic temps/strip crowns - at the Center for Pediatric Dentistry, Seattle, Washington.

4. STUDY DESIGN

This pilot study is a single-center, non-blinded, controlled clinical trial with evaluations at baseline; follow up assessments at months 3, 6, 12 and 18; and a final assessment at the end of study visit occurring at 24.

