7. STUDY PROCEDURES

7.1 Training

All research study team members will obtain clinical research and HIPAA training prior to start of study. All pediatric dental (PEDO) clinician team who work at the Dental Surgery Center (DSC) and are willing to participate in this study will train with the NuSmile crowns by preparing extracted or typodont primary teeth and cementing the crowns and at least six *in vivo* cases done under general anesthesia for each crown type in the study. Intra and inter-reliability assessment will be obtained ($\text{Kappa} > 0.8$). Training and calibration will be performed by a representative from NuSmile and [name] from the Center for Pediatric Dentistry.

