7.4 Treatment Randomization

Restorations will be randomly allocated to a patient; all teeth in a single patient will be randomly allocated to receive one of the restoration treatments: 1) NuSmile Signature crowns (thirty patients in the intervention group 2) NuSmile ZR crowns (thirty patients in the intervention group and 3) and composite strip crowns (thirty patients in control group).

The randomization sequence will be created using STATA 12.0 (StataCorp, College Station, TX) statistical software using random block sizes, which are known only to the study statistician. The randomization list will be created and placed in the order determined above into opaque sealed envelopes prior to trial start. The envelopes will be kept in a secure place known only to the study coordinator, research assistants, and statistician.

Each patient will be assigned a random treatment when they arrive at the treatment appointment and after they have been determined eligible and have signed the consent form. The clinician will be told the treatment assignment immediately prior to the treatment appointment.

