8. CLINICAL ASSESSMENTS

Clinical Assessments for both groups will be done at post crown placement (baseline); and months 3, 6, 12, and 18; and end of study visit occurring in range of 24 to 30 months from baseline. Please see Appendix 3 for scoring Criteria for the following:

- Fit
- Positioning
- Proximal Contact
- Marginal Adaptation
- Color: Match, staining/color change
- Gingival Status
- Retention of the crown
- Integrity of the veneer/composite
- Secondary Caries
- History of trauma
- Clinical pulp pathology
- Radiographical pulp pathology
- Parents' esthetic satisfaction

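### The maker of two of the three crowns shares in rater calibration, and nothing separates assessor from operator, so product preference can bias the judgement-based grades in this open trial

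*Combined protocol and SAP*

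**What the plan says.** Section 4 describes a "single-center, non-blinded, controlled clinical trial" and makes no exception for outcome assessors. Section 7.4 randomizes by patient and adds: "The clinician will be told the treatment assignment immediately prior to the treatment appointment".

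Section 7.1 concerns the pediatric dental clinicians who place the crowns. They "will train with the NuSmile crowns by preparing extracted or typodont primary teeth" and complete at least six supervised-type cases in patients for each crown type. The same paragraph continues "Intra and inter-reliability assessment will be obtained", with kappa above 0.8, and then "Training and calibration will be performed by a representative from NuSmile and" one named person from the Center. Section 3 sets out the comparison: "Pre-Veneered Stainless Steel Crown – NuSmile Signature and NuSmile ZR compared with composite crowns". Both test crowns are therefore NuSmile products and the control is not.

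Section 8 opens "Clinical Assessments for both groups will be done at post crown placement (baseline" and goes on to list visits and items. Section 10 repeats the schedule item by item. Neither names an assessor role, separates assessor from operator, or provides for independent reading of the photographs or radiographs. Section 11 lists 13 primary efficacy variables and plans significance tests between arms at baseline and at 6, 12, 18 and 24 months.

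**The concern.** Several primary variables are graded by judgement. Appendix 1 separates good from moderate retention, Appendix 4 turns on whether a detectable margin defect is acceptable, Appendix 5 on whether a shade is close enough, and the first steps of Appendix 7 on redness. A rater who can see the crown type, and whose scoring standard was set partly by the maker of that crown, may resolve borderline cases in one direction. Randomization balances the children, not the measurement, and a larger sample does not remove a measurement bias.

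This matters because Section 2 justifies the trial by saying that the existing evidence comes largely from bench work and operator experience. If operators may grade the crowns, with a maker's representative taking part in calibration, some of that weakness returns. Pilot status does not settle the matter, since Section 11 tests these scores between arms.

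**Working it through.** The plan gives no figure to reproduce here. The sample of 90 (3 × 30) is a convenience sample with no power inputs. The check has a reading part and an illustrative part.

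**Reading.** The only clinicians whose training is described are those who place crowns (7.1). The reliability requirement is in that paragraph, and no other examiner group appears in the document. The natural reading is that raters come from the placing team; at the least, nothing prevents it. The sentence on who calibrates follows directly on the kappa requirement, so it is naturally read as covering the rating exercise as well as placement technique.

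**Size of a false difference.** All rates are assumptions. Let p be the true share of crowns meriting a grade below A, equal in all arms, and f the share of those upgraded to A in the two NuSmile arms only. The observed rate is p(1 − f) in those arms and p in the control, so the false difference is p × f.

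| p | f | NuSmile arms | Control | False difference |
|---|---|---|---|---|
| 20% | 10% | 18% | 20% | 2 points |
| 20% | 25% | 15% | 20% | 5 points |
| 40% | 10% | 36% | 40% | 4 points |
| 40% | 25% | 30% | 40% | 10 points |

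**Would kappa > 0.8 catch it?** Compare the biased rater with an unbiased one, on A versus not A, with the three crown types in equal numbers, p = 40% and f = 25%:
- Disagreement: 0.40 × 0.25 × 2/3 = 0.067, so observed agreement is 0.933.
- Biased rater's non-A rate: 0.40 × (1 − 0.25 × 2/3) = 0.333.
- Chance agreement: 0.40 × 0.333 + 0.60 × 0.667 = 0.533.
- Kappa: (0.933 − 0.533)/(1 − 0.533) = 0.86, which passes.

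At p = 20% and f = 25% the same steps give (0.967 − 0.700)/(1 − 0.700) = 0.89. On NuSmile crowns alone at p = 40%, agreement is 0.90 and chance agreement 0.40 × 0.30 + 0.60 × 0.70 = 0.54, so kappa = 0.36/0.46 = 0.78, just short of the threshold. Thus kappa might flag the bias if it were computed by crown type against an unbiased rater, which the plan does not ask for. Two raters who share the same bias can agree perfectly in either case.

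**Contribution of self-scoring alone.** If every operator is equally lenient towards his or her own work, f applies in all three arms. At p = 40% and f = 25% each arm reads 40% × 0.75 = 30%, and the false difference is 0. The table therefore depends on leniency that differs by crown type.

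**The case against.** The strongest reply is that self-scoring is not the mechanism. Clinicians train on every crown type and patients are randomized, so an operator's own crowns fall in all three arms. Leniency towards one's own work is then expected to be similar across arms. This stands: only preference between products, or a scoring standard tilted towards one maker, moves the contrast. It also limits the fix, because a colleague from the same team still sees the crown type.

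Second, three stronger readings are tempting and should be set aside.
- A reader might infer that operators will score their own crowns and that the grades are therefore biased. The document does not say who scores.
- A reader might infer that the manufacturer alone calibrates. Section 7.1 makes the role joint with a Center member and sets a kappa threshold.
- A reader might infer that NuSmile is the sponsor. Section 9 mentions a study sponsor without identifying it.

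Third, Section 7.1 does not spell out that the manufacturer's representative sets scoring standards; the training it describes is tooth preparation and cementation. The link to scoring comes from the word calibration and the adjoining kappa sentence. This is a fair reading but not an explicit statement, and the text should settle it.

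Fourth, exposure is uneven. A missing crown, veneer loss recorded by thirds and bleeding on probing have observable anchors. Esthetic satisfaction is rated by parents and lies outside this mechanism, although parents are not masked either.

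These points narrow the concern. They do not answer why the maker of two arms should share in calibrating raters, or why the assessor is left unspecified.

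**Conclusion.** The concern holds as a risk of bias: the stated calibration arrangement and the unspecified assessor can bias the arm comparison on judgement-based grades, through product preference or a shared standard that favours the maker's crowns. The documents do not show that such bias will occur, and its size and direction are unknown. The illustrative 2 to 5 points (true non-A rate 20%) and 4 to 10 points (40%) assume no true difference and upgrading of 10% to 25% confined to the NuSmile arms; neither assumption comes from the plan. The kappa requirement is a check on agreement and cannot be relied on as a safeguard here. The text should be changed, because the remedy is cheap and the problem cannot be repaired in analysis if the assessor is not recorded.

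**What to change.** In Section 7.1, limit the manufacturer's representative to training in crown placement, and have the Center's trainer alone lead scoring calibration and the kappa exercise. State which people and which scales the kappa requirement covers.

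In Sections 8 and 10, require that follow-up scores come, where staffing allows, from an already calibrated team member who did not place that child's crowns. Record assessor and operator for every score, baseline included, so that the extent of self-scoring can be reported.

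The cost is mainly scheduling: recall booking becomes less flexible. Sample size, visits and treatment do not change. The number of calibrated clinicians is not given, hence the staffing qualification. Because crown type remains visible at examination, the change lowers the risk of bias but does not remove it.
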